 exception of acetaminophen (paracetamol), during the 7 days before
 the first dose of trial medication
- Use of dietary supplements or herbal remedies (such as St John's Wort) known to interfere with the CYP3A4 and/or P-gp metabolic pathways during the 28 days before the first dose of trial medication (see list in Study Procedures Manual)
- Relevant pathological abnormalities in the ECG such as a second or third-degree AV block, prolongation of the QRS complex over 120 msec or of the QTc-interval over 450 msec (QTcB or QTcF)
- Subjects testing positive in the drug screening
- Excluded therapies which may impact on the interpretation of study results in the opinion of the investigator or sponsor
- Objection by General Practitioner (GP) to subject entering trial
- History of residing for 6 or more continuous months, within the last 3 years, in regions with endemic parasitic infections as determined by the investigator
- Possibility that subject will not cooperate with the requirements of the protocol

The following exclusion criteria are applicable only to subjects in Cohort 10:

- No contact lenses wear within 1 month prior to dosing. Contact lenses wear is not permitted during the study.
- Any ocular disorder for which topical ocular therapy is currently or

chronically prescribed, including inflammatory eye disease (dry eye allergic conjunctivitis [seasonal allergic conjunctivitis, vernal keratoconjunctivitis, atopic keratoconjunctivitis], uveitis and glaucoma)

- Past history of ocular disease requiring ongoing treatment
- Past ocular surgery including laser or other refractive corneal surgery
- Evidence of eye irritation, visual difficulties, corneal opacity, ocular surface (corneal or conjunctival damage, with or without ocular symptoms)
- Evidence of narrow anterior chamber angles causing increased risk of acute glaucoma
- Evidence of ocular media opacity including lens opacity/vitreous opacities
- Evidence of retinal or optic nerve pathology
- Evidence of pronounced colour blindness, as indicated by an Ishihara score of 9/13 or below

Subjects must not expose themselves to sunlight (eg, go out of doors) for longer than 15 minutes without using a strong sunblock (sun protection factor (SPF) 30 or above), or use a sunbed, or expose themselves to other sources of UV light, while they are taking emodepside and until 3 days after their last dose.

Removal of subjects from study

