The predicted human CL is low for both species used for prediction. The differences in predicted human clearance ranging from 0.11 (rat) to 0.14 L/(kg·h) (dog) are minor. With the Cb/Cp distribution of 0.6 values for CLblood would be 0.18 (rat) and 0.23 (dog), respectively. These predictions are in the same range as the human clearance obtained in vitro in hepatocytes (CLblood = 0.36 L/(kg·h)). The predicted volume of distribution in man is high covering a range of 15 L/kg (rat) to 11 L/kg (dog). However, individual parameters for volume (Vc, Vt1 and Vt2) showed differences according to the species used for prediction. Consequently, the C/t profiles predicted for man mainly differ in C_{max} and t_{max} . The value for the absorption rate constant (ka, 0.8 h-1) was based on former experiences with PEG-based liquid service formulations. The bioavailability obtained from the animal species was directly used for the prediction of the human plasma concentration profiles.

Description of the theoretical dose levels to be studied is presented in Table 2:

Table 2. Study Treatment: Formulation and Dose-Levels by Cohort

Part	Cohort	Formulation	Do	ose	Increase from
			Total mg	mg/kg ^a	Previous Dose
	Cohort 1	LSF solution	1.0	0.014	
	Cohort 2	LSF solution	2.5	0.036	+ 150%
	Cohort 3	LSF solution	5.0	0.071	+ 100%
1	Cohort 4	IR tablet	5.0	0.071	+ 100%
'	Cohort 5	LSF solution	10.0	0.143	+ 100%
	Cohort 6	LSF solution	20.0	0.286	+ 100%
	Cohort 7	IR tablet	20.0	0.286	+ 100%
	Cohort 8	LSF solution	40.0	0.571	+ 100%
2 ^b	Cohort 9	LSF solution (fed)	10.0	0.143	Not applicable
	Cohort 10	LSF solution	40.0	0.571	Not applicable

^a Dose levels are theoretical, as calculated based on an average weight of 70kg.

^b Part 2 (Cohorts 9 and 10) are considered exploratory

4. Selection of Subjects

The following eligibility criteria were designed to select healthy male subjects aged 18 to 55, selected from the panel of volunteers recruited by HMR, for whom the protocol treatment is considered appropriate. All relevant medical and non-medical conditions should be taken into consideration when deciding whether this protocol is suitable for a particular subject. Eligibility criteria may not be waived by the Investigator. Any questions regarding a subject's eligibility should be discussed with the Sponsor's Medical Expert prior to subject's enrolment.

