4.2. Exclusion Criteria

The presence of any of the following will exclude a subject from study enrolment:

- 1. Participation in another clinical trial within 3 months prior and during the study, or 5-times the half-life of the drug tested in the previous clinical trial, whichever is longer (time calculated relative to the last dose in the previous clinical trial)
- Clinically relevant abnormal medical history, concurrent medical condition, acute or chronic illness or history of chronic illness sufficient to invalidate the subject's participation in the trial or make it unnecessarily hazardous.
- 3. Surgery (eg stomach bypass) or medical condition that might affect absorption of study drug taken orally.
- 4. Presence of abnormal physical findings, ECG, or laboratory values at the pre-trial screening assessment that could interfere with the objectives of the trial or the safety of the subject.

- Relevant pathological abnormalities in the ECG such as a second or thirddegree AV block, prolongation of the QRS complex over 120 msec or of the QTc-interval over 450 msec (QTcB or QTcF)
- 6. Blood pressure and heart rate in supine position at the screening examination outside one (or more) of the ranges:
 - 90–140 mm Hg systolic
 - 60-90 mm Hg diastolic
 - heart rate 40-100 beats/min

Subjects with vital signs outside the reference range for the population being studied may be included, at the investigator's discretion, if it is unlikely to introduce additional risk factors and will not interfere with study procedures.

- 7. History of relevant diseases of vital organs, of the central nervous system or other organs
- 8. Subjects with a medical or psychiatric disorder, condition or history of such that would increase the risk associated with study participation, or impair the subject's ability to participate or complete this study, in the opinion of the investigator or the sponsor
- 9. Subjects with a history of severe allergies, non-allergic drug reactions, severe adverse reaction to any drug, or multiple drug allergies
- 10. Subjects with a hypersensitivity to the investigational drug, the control agent and/ or to inactive constituents
- 11. Positive tests for hepatitis B & C, HIV
- 12. Subjects testing positive in the drug screening
- 13. Presence or history of drug or alcohol abuse during the last 10 years, or intake of more than 21 units of alcohol weekly.
- 14. Regular daily consumption of more than one liter of xanthine-containing beverages

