- 15. Regular daily consumption of more than 5 cigarettes daily, or use more than 3 grams (1/8 ounce) of tobacco
- 16. Use of a prescription medicine during the 28 days before the first dose of trial medication or use of an over-the-counter medicine, with the exception of acetaminophen (paracetamol), during the 7 days before the first dose of trial medication
- 17. Use of dietary supplements or herbal remedies (such as St John's Wort) known to interfere with the CYP3A4 and/or P-gp metabolic pathways during the 28 days before the first dose of trial medication (see list in Study Procedures Manual)
- 18. Excluded therapies which may impact on the interpretation of study results in the opinion of the investigator or sponsor
- 19. Febrile illness within 1 week before the start of the study
- 20. Objection by General Practitioner (GP) to subject entering trial.
- 21. Loss of more than 400 mL of blood within the previous 3 months

- 22. History of residing for 6 or more continuous months within the last 3 years, in regions with endemic parasitic infections as determined by the investigator
- 23. Possibility that subject will not cooperate with the requirements of the protocol

Part 2, Cohort 10:

The following exclusion criteria are applicable only to those subjects:

- 24. No contact lenses wear within 1 month prior to first dose of IMP. Contact lenses wear is not permitted during the study
- 25. Any ocular disorder for which topical ocular therapy is currently or chronically prescribed, including inflammatory eye disease (dry eye allergic conjunctivitis [seasonal allergic conjunctivitis, vernal keratoconjunctivitis, atopic keratoconjunctivitis], uveitis and glaucoma)
- 26. Past history of ocular disease requiring ongoing treatment
- 27. Past ocular surgery including laser or other refractive corneal surgery
- 28. Evidence of eye irritation, visual difficulties, corneal opacity, ocular surface (corneal or conjunctival damage, with or without ocular symptoms)
- 29. Evidence of narrow anterior chamber angles causing increased risk of acute glaucoma
- 30. Evidence of ocular media opacity including lens opacity/vitreous opacities
- 31. Evidence of retinal or optic nerve pathology
- 32. Evidence of pronounced colour blindness, as indicated by an Ishihara score of 9/13 or below ¹³

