### **11.2 Protocol Deviations**

Before closing the database, data listings will be reviewed to identify any significant deviations and determine whether the data should be excluded from any analysis populations.

Major protocol deviations include subjects who:

- Entered the study even though they did not satisfy the entry criteria.
- Met the criteria for withdrawal from the study but were not withdrawn.
- Received the wrong treatment or incorrect dose.
- Received an excluded concomitant therapy.
- Received investigational product(s) past the expiration date and time.

- Had their treatment assignment unblinded.

In addition, subjects with minor time deviations (measurements taken outside the allowable windows given in the protocol) will be identified.

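### Cohort 10 exclusion criterion 24 (contact lenses) has reversed polarity: read literally, it excludes non-wearers and does not exclude recent wearers

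*Protocol*

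**What the plan says.** Section 4.2 of the Protocol sets one rule for the whole exclusion list: "The presence of any of the following will exclude a subject from study enrolment". Criteria 24 to 32 apply to Cohort 10 only, and criterion 24 begins "No contact lenses wear within 1 month prior to first dose of IMP". A second sentence follows within the same item: "Contact lenses wear is not permitted during the study".

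The Protocol Summary, under Main Entry Criteria, repeats the pair. Its lead-in is "The following exclusion criteria are applicable only to subjects in Cohort 10", and its first item is "No contact lenses wear within 1 month prior to dosing", again followed by the ban on lenses during the study.

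Three other provisions bear on the point:

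- The opening paragraph of Protocol Section 4 states "Eligibility criteria may not be waived by the Investigator". It then sends questions about a subject's eligibility to the sponsor's medical expert before enrolment.
- Protocol Section 8.2 does not allow rescreening of subjects who failed screening on the inclusion or exclusion criteria.
- SAP 11.2 counts among major protocol deviations subjects who "Entered the study even though they did not satisfy the entry criteria", and calls for a review of the listings before the database is closed.

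**The concern.** An exclusion list works only if each entry describes the state that keeps a subject out. Criterion 24 describes the state the sponsor wants subjects to be in. Combined with the lead sentence, it says the reverse of what its own second sentence implies.

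What is at stake is the integrity of an eligibility rule in the one cohort set up to look at the eye. A site that follows the text exactly would turn away the intended subjects and would not use this item to turn away recent wearers. A site that follows the evident intent departs from the wording of an approved criterion that it has no authority to waive. Any later check of enrolled subjects against the literal text would then show a discrepancy for each non-wearer.

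**Working it through.** No arithmetic applies and the plan gives no figure to reproduce. The check is a logical reading of the text.

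**Inputs**

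1. Rule (Protocol 4.2, lead sentence): a subject is excluded if any listed item is present.
2. Item (Protocol 4.2, criterion 24; same content in the Summary): no lens wear in the month before dosing.
3. Second sentence of the item (both places): lens wear is barred during the study.

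**Applying the rule to the item**

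| Subject in the month before dosing | Item 24 present, as written? | Result as written | Result with the leading No removed |
|---|---|---|---|
| No lens wear | Yes | Excluded | Not excluded by this item |
| Lens wear | No | Not excluded by this item | Excluded |

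The last column agrees with the second sentence of the item; the column as written does not. It would make little sense to shut out those who already go without lenses, leave recent wearers eligible, and then forbid lenses to everyone enrolled.

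**Comparison with the neighbouring items.** Criteria 24 to 32 make nine Cohort 10 items (32 − 24 + 1 = 9). The other eight all name a condition whose presence should exclude, for example criterion 27, "Past ocular surgery including laser or other refractive corneal surgery". Criterion 24 is the only one that runs the other way, so this is a slip in one item and not a different drafting convention for the list.

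**Is it corrected elsewhere?** The Summary and Section 4.2 carry the same negation, so neither can be used to correct the other. The Cohort 10 paragraph of Section 4.3 covers distance glasses, mydriatic drops and driving, but does not mention lenses. The SAP does not restate the criterion. No place in either document gives the lens rule with the right polarity.

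**The case against.** The strongest reply is that nobody would misapply this. The ban on lenses during the study sits in the same item, and Section 4.3 tells Cohort 10 subjects to bring distance glasses if they have them. Section 4 also gives a route for doubtful cases, since eligibility questions go to the sponsor's medical expert. The list is not drafted for strict literal parsing in any case: criterion 6 contains its own discretionary clause. All of this stands, and it is why the practical risk is low. It does not make the text right, because consulting the medical expert settles a single case and leaves the approved criterion as it is.

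Four stronger readings are tempting, and the documents do not support them.

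- **All eight subjects are affected.** A reader might infer that either the whole cohort consists of recent wearers or the whole cohort is in breach. That leaves out the likeliest outcome: the site applies the evident intent, records the criterion as satisfied and logs no deviation. It also leaves out a mixed cohort.
- **Stopping lenses would confound the eye findings.** A reader might infer that refraction or the eye surface would shift between the screening examination and Day 0. The documents neither state such a shift nor give its size. Criterion 28 separately excludes eye irritation, visual difficulties and corneal or conjunctival damage, and the cohort has randomised placebo subjects, although only two are planned.
- **Data would be lost.** A reader might infer that a criterion 24 deviation removes a subject from analysis. SAP 11.2 only prompts a review of whether data should be excluded. SAP Section 8 defines no per-protocol set, and the ophthalmology summary (Table 14.3.10) uses the Safety Population, which is everyone dosed.
- **This is a choice of design.** A reader might infer that the sponsor meant to select wearers. The item's second sentence rules that out.

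**Conclusion.** The criterion is wrong as written. It is a drafting error in an operative, non-waivable eligibility rule, it occurs in two places, and nothing in the Protocol or SAP corrects it. Read literally, it excludes subjects without lens wear in the month before dosing and fails to exclude those with it. The word *fails* is deliberate: the item does not admit recent wearers outright, because the other eight eye criteria still apply to them.

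The consequence is modest. If the text is applied literally to the enrolled cohort, each intended non-wearer is an entry-criteria deviation to be listed and reviewed under SAP 11.2. How many subjects that would be depends on how the site reads the item, which the documents do not settle, so no count is given here.

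The conclusion rests on one assumption about intent, that the sponsor wanted subjects free of lenses for the month before dosing. The ban during the study supports this directly. The correction is worth making because it costs almost nothing and brings an approved criterion into line with what the site is expected to do.

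**What to change.** Delete the leading word No in both places, so that lens wear in the preceding month becomes the excluding condition:

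- Protocol Summary, Cohort 10 exclusions: *Contact lens wear within 1 month prior to dosing*.
- Protocol 4.2, criterion 24: the same change, keeping that section's reference to the first dose of IMP.

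The sentence barring lenses during the study can stay where it is. It is a conduct rule, so repeating it in or moving it to the Cohort 10 paragraph of Section 4.3 would be tidier, but this is optional.

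The cost is one word removed in two places through the Protocol's own amendment process. No subjects, procedures or analyses are added, and the SAP needs no change.

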1.1. Background Information

Filarial diseases cover infectious diseases caused by parasitic nematode worms onchocerciasis (river blindness), lymphatic filariasis (LF, or elephantiasis), and loiasis (African eye worm, or *Loa loa*). More than 1 billion of the world's poorest people are at risk. ^{24,25} An estimated 120 million people suffer from LF, and about 80% of people at risk live in the following 10 countries: Bangladesh, Democratic Republic of Congo, Ethiopia, India, Indonesia, Myanmar, Nigeria, Nepal, Philippines, and the Republic of Tanzania. ²⁵ Loiasis occurs exclusively in West and Central Africa, where an estimated 13 million are infected with *Loa loa*. ¹² An estimated 37 million ²⁰ suffer from onchocerciasis, with 99% cases in 31 African countries, and 169 million at risk. Although the disease is almost exclusively confined to West and Central Africa, some foci exist in Yemen and South America (Brazil and Venezuela). ^{12,23}

The burden associated to onchocerciasis is estimated at nearly 600'000 disability-adjusted life years (DALYs) worldwide. Severe visual impairment and blindness are considered the most severe complication of the disease and their control was the main objective of the initial control programs in West Africa (OCP). However skin lesion and itching represent a significant public health problem in affected communities. Incessant itching may cause insomnia, affects work productivity and social relationships and can even induce a premature child weaning by affected mothers. Onchocerciasis is still the world's second-leading infectious cause of blindness. The World Health Organization (WHO) estimates that 746'000 patients are visually impaired, 265'000 are blinded and more than 4 million suffer from severe itching.

Onchocerca is a helminth of the genus nematode (roundworm), causing onchocerciasis in humans. The disease is contracted through the bite of an infected vector, a female blackfly of the genus *Simulium*, which transmits infective larvae to a person. Once injected in the host, the larvae molt twice before reaching adult stage. An adult worm can then live for 15 years in the human body. An adult worms settle into fibrous nodules in the human body close to the surface of the skin or near the joints. Adult male migrates from nodule to nodule. After mating, a female releases about 1,000 new microfilariae per day. The microfilariae migrate through the skin where they are eventually ingested by a blackfly in which the parasite completes its life cycle by molting twice into an infective larvae. These larvae may then be transferred to another host to continue the cycle.

Clinical Manifestations

Infection with *O. volvulus* can result in initial symptoms such as fever, neuralgic pain in joints, and temporary hives on the trunk and face. Pruritus is the most common early symptom of onchocerciasis. It usually develops after a latent or "prepatent" interval of 1 to 2 years following initial infection. Some infected persons remain asymptomatic (about 10% of cases) or can develop symptoms during the course of the infection (which last up to 14 years). Inflammatory responses due to dead or

dying microfilaria are responsible for the majority of the clinical manifestations, which can range from the dermatological to the ocular symptoms, briefly described below.

Dermatological Symptoms

Onchoceral Dermatitis is the most common symptom of the disease. The condition can appear anywhere on the body and usually begins with intense itching. A rash consisting of patches of papules can appear on the body at any time and often leads to incessant scratching. In West Africa, this condition is known as craw-craw. This acute dermatitis may progress into chronic dermatitis with large papules and, in a later stage, hyper-pigmentation and the thickening of the skin, popularly known as Lizard skin. More advanced stage is characterized by loss of elasticity, atrophy of the skin and depigmentation known as Leopard skin. ¹⁵

Onchocercomas are subcutaneous, fibrous nodules where adult worms dwell and breed. These nodules are most easily felt when they form over a bony part of the body. The location of the nodules on the body depends on the place that the fly bites, which varies by region. In America, the nodules are mostly found on the upper body in the head and neck region, whereas in Africa the nodules are mostly on the lower body, especially in the groin region. It is estimated that only 30% of existing nodules can be found by palpation (95% CI 16-41%).

Ocular Symptoms

Ocular symptoms are severe reactions that occur only after several years of having the disease. Initially, dead microfilariae in the eye cause inflammation and keratitis. Then, if the infection persists over a number of years, sclerosing keratitis, iridocyclitis, chorioretinitis, and uveitis occur, resulting in permanent visual impairment, glaucoma, or blindness. It is estimated that the life expectancy of a person who becomes blind in endemic areas may be shortened by up to 10 years. ¹⁹

Diagnosis

Standard diagnosis of onchocerciasis is made by examination for microfilariae in skin biopsies. This technique has low sensitivity in light infections and it is an invasive method with low acceptability among the population. Infection in the eyes can be diagnosed with a slit-lamp examination to detect microfilaria and onchocerciasis lesions. In patients presenting subcutaneous nodules, adult worms can be found inside the nodules surgically removed. Other diagnostic methods are PCR-based diagnosis of skin scrapings for *O. volvulus*, more sensitive than parasitological examination of skin snips, and Ov-16 antibody detection card tests or diethylcarbamazine (DEC) patch test.

Treatment

Ivermectin (150 mg/kg single, oral dose) is the standard treatment of onchocerciasis patients. The drug kills the microfilarial stage of the parasite and includes temporary sterilization of adult female worm, reducing disease transmission and morbidity. However, the drug fails to kill adult worms, as a consequence, onchocerciasis requires treatments for up to 15 years (the life span of adult worms), to eliminate the parasite from the body.

Programs directed by the WHO for the treatment and control of onchocerciasis have been in place for over twenty years. The African Program for Onchocerciasis Control (APOC) spans 24 countries in Central and Western Africa. The treatment approach is preventive chemotherapy based on the administration of ivermectin once or twice a year to all the population in endemic areas.

In areas of Loa loa co-infection, serious adverse events (SAE) following the use of ivermectin were observed. The most severe complication is an encephalopathy which is triggered by the massive death of microfilariae that can be fatal or leave long-term sequelae. SAEs happen in 1 in 10'000 treatments among patients with high Loa loa parasitemia in Western and Central Africa (Angola, Cameroon, Democratic Republic of Congo, South Sudan) where onchocerciasis and loiasis are often co-endemic (The Mectizan Expert Committe and the Technical Consultative Committee, 2004). Geographical areas in which prevalence of *Loa loa* is higher than 20% are considered as high risk for encephalopathy. These areas have been defined through an epidemiological survey called Rapid Assessment Procedure for *Loa Loa* (RAPLOA). In these areas the risk of SAEs is particularly high when mass drug administration (MDA) programs are implemented for the first or second time when microfilariae prevalence is highest within the treated population.

Rationale for the Development of Emodepside

The programs for the treatment and control of filarial diseases through MDA have been in place for over 20 years with an important success in reducing transmission and morbidity. However, current treatments must be repeated at regular intervals for the life of the adult worm (up to 15 years), making implementation extremely difficult in endemic countries.

Additionally, the programs have to be implemented with special measures in regions of Onchocerca infection where patients are co-infected with Loa loa. This limits the use of ivermectin in MDA programs in co-endemic areas, and is an impediment to achieving WHO elimination goals for onchocerciasis. Furthermore, reports of a suboptimal parasite response to ivermectin may be a sign of developing resistance.¹⁶

Thus, there is an urgent need for a macrofilaricide, targeting onchocerciasis worms for use in individual case management and, after appropriate testing, as an alternative treatment in MDA programs. A macrofilaricidal drug could reduce the number of MDA cycles needed thereby easing program implementation and enhancing chances of disease elimination, particularly in Loa loa co-endemic areas.

Emodepside (synonym: BAY 44 4400) is a cyclooctadepsipeptide anthelmintic drug stimulating presynaptic receptors belonging to the secretin receptor family, resulting in flaccid paralysis of parasitic nematodes. Emodepside also interacts with SLO-1, a calcium activated potassium channel. Emodepside is a registered drug for animal health, commercialized by Bayer Health Care under the name of Profender[®] (in combination with praziquantel) or Procox[®] (in combination with toltrazuril) indicated for treatment of *Toxocara cati*, *Toxocara canis*, *Toxascaris leonina*, *Uncinaria stenocephala*, *Trichuris vulpis* and *Ancylostoma tubaeforme* infections. Emodepside is a semi-synthetic drug with the precursor isolated as fermentation products from *Mycelia sterilia*, a fungus that grows on leaves of *Camellia japonica*.

Emodepside was shown to be macrofilaricide against a variety of filarial nematodes as investigated in both in vitro and in vivo studies: *Achatocheilonema viteae*, *Litomosoides sigmodontis*, *Brugia malayi*, *Onchocerca gutturosa*, *Onchocerca lienalis*. These filarial models are the accepted models for filarial diseases in humans.³

In conclusion, emodepside targets different life stages of helminths parasites including the adult stage. This is a very important feature since treatments targeting *Onchocerca* adult worms have the potential to eliminate infection. Hence, emodepside can be considered as promising drug candidate able to fulfill unmet medical needs for the treatment of onchocerciasis.

There are currently no drugs targeting the adult stage of *Onchocerca* parasites in humans. Therefore the clinical development plan will consider a number of clinical endpoints to assess the effect of emodepside in humans.

